#### *Immune-mediated hepatitis*

Monitor subjects for changes in liver function (at the start of treatment, periodically during treatment and as indicated based on clinical evaluation) and symptoms of hepatitis, and exclude other causes of hepatitis.

Administer corticosteroids (initial dose of 0.5 – 1.0 mg/kg/day for grade 2 events, and 1 – 2 mg/kg/day for grade 3 or greater events, of prednisone or equivalent, followed by a taper) and, based on severity of liver enzyme elevations, withhold or discontinue pembrolizumab.

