#### *Immune-mediated nephritis*

Monitor patients for changes in renal function and exclude other causes of nephritis. Administer corticosteroids for grade 2 or greater events (initial dose of 1 – 2 mg/kg/day prednisone or equivalent, followed by a taper), withhold pembrolizumab for moderate (Grade 2), and permanently discontinue pembrolizumab for severe (Grade 3) or life-threatening (Grade 4) nephritis.

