## 6.6 Supportive Care Guidelines for Pneumonitis

Patients with symptomatic pneumonitis should immediately stop receiving pembrolizumab and have an evaluation. The evaluation may include bronchoscopy and pulmonary function tests to rule out other causes such as infection. If the patient is determined to have study drug associated pneumonitis, the suggested treatment plan is detailed in Table 11.

**Table 11:** Recommended Approach to Handling Pneumonitis

Study drug associated pneumonitis	Withhold/Discontinue Pembrolizumab?	Supportive Care
Grade 1 (asymptomatic)	No action	Intervention not indicated
Grade 2	Withhold pembrolizumab, may return to treatment if improves to Grade 1 or resolves within 12 weeks Second episode of pneumonitis – discontinue pembrolizumab if upon re-challenge the patient develops a second episode of Grade 2 or higher pneumonitis.	Consider pulmonary consultation with bronchoscopy and biopsy/BAL. Conduct an in person evaluation approximately twice per week Consider frequent Chest X-ray as part of monitoring Treat with systemic corticosteroids at a dose of 1 to 2 mg/kg/day prednisone or equivalent. When symptoms improve to Grade 1 or less, steroid taper should be started and continued over no less than 4 weeks. Consider antibiotics
Grade 3 and Grade 4	Discontinue pembrolizumab	Hospitalise patient Bronchoscopy with biopsy and/or BAL is recommended. Immediately treat with intravenous steroids (methylprednisolone 125 mg IV). When symptoms improve to Grade 1 or less, a high dose oral steroid (prednisone 1 to 2 mg/kg once per day or dexamethasone 4 mg every 4 hours) taper should be started and continued over no less than 4 weeks. If IV steroids followed by high dose oral steroids does not reduce initial symptoms within 48 to 72 hours, treat with additional anti-inflammatory measures. Discontinue additional anti-inflammatory measures upon symptom relief and initiate a prolonged steroid taper over 45 to 60 days. If symptoms worsen during steroid reduction, initiate a re-tapering of steroids starting at a higher dose of 80 or 100mg followed by a more prolonged taper and administer additional anti-inflammatory measures, as needed add prophylactic antibiotics for opportunistic infections. The use of infliximab may be indicated as appropriate.

For Grade 2 pneumonitis that improves to  $\leq$  Grade 1 within 12 weeks, the following rules should apply:

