## 11.5 Appendix 5 - Identification, Evaluation and Management of immune related events of clinical interest (irECIs)

ECI	Grade	Action to be taken	Supportive Care
Pneumonitis –	Grade 1 (Asymptomatic)	
 
No action
 
	
 
Intervention not indicated
 

	Grade 2	
 
Report overdose and liver toxicity ECIs within 24 hours
 
Withhold pembrolizumab, may restart if Grade 1 or resolved within 12 weeks
 
Consider bronchoscopy and biopsy/BAL, ID Consult and frequent chest x-ray for monitoring.
 
Conduct in person evaluation twice a week
 
	
 
1-2mg/kg/day prednisone or equivalent.
 
Symptoms grade 1 or less, initiate steroid taper for no less than 4 weeks.
 
Permanently discontinue pembrolizumab if dose cannot be reduced to 10mg prednisone or less or equivalent per day within 12 weeks.
 

	Grade 3 and 4	
 
Report overdose and liver toxicity ECIs within 24 hours
 
Discontinue pembrolizumab
 
Hospitalise patient
 
Bronchoscopy with biopsy and/or BAL is recommended.
 
	
 
methylprednisolone 125mg IV.
 
Symptoms grade 1 or less initiate steroid taper for no less than 4 weeks 
 
Prednisone 1 to 2 mg/kg/day or dexamethasone 4mg every 4 hours
 
 
 
If IV steroids do not reduce initial symptoms within 48-72 hours treat with additional anti-inflammatory measures. At symptom relief discontinue anti-inflammatory and start steroid taper over 45-60 days. If symptoms worsen during this period refer to Section 6 and 7.
 

 
1st episode - May increase dosing interval by one week in subsequent cycles
 
2nd episode of - Pneumonitis, permanently discontinue pembrolizumab if upon re-challenge patient develops Pneumonitis ≥ Grade 2
 
			
Colitis	Grade 1 (Asymptomatic)	
 
No action
 
	
 
Intervention not indicated
 

–			

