		
 
Report overdose and liver toxicity ECIs within 24 hours
 
Withhold pembrolizumab, may restart if Grade 1 or resolved within 12 weeks
 
Symptomatic treatment 
 
Consider GI consult & endoscopy to rule out colitis
 
 
 
	
 
Prednisone 1-2mg/kg/day or equivalent
 
Symptoms grade 1 or less, initiate steroid taper for no less than 4 weeks.
 
Permanently discontinue pembrolizumab if dose cannot be reduced to 10mg or less of prednisone or equivalent per days within 12 weeks.
 
If symptoms worsen or persist >1 week treat as grade 3.
 

		
 
• Report overdose and liver toxicity ECIs within 24 hours
 
• Withhold pembrolizumab
 
• Rule out bowel perforation
 
• Recommend gastroenterologist consult & biopsy with endoscopy
 
	
 
• methylprednisolone 125mg IV followed by prednisone 1 to 2 mg/kg/day or dexamethasone 4mg every 4 hours.
 
• Symptoms grade 1 or less initiate steroid taper for no less than 4 weeks.
 
• Taper 6-8 weeks in patients with diffuse or severe ulceration and/or bleeding
 
• If IV steroids do not reduce initial symptoms within 48-72 hours treat with additional anti-inflammatory measures. At symptom relief discontinue anti-inflammatory and initiate steroid taper over 45-60 days. If symptoms worsen during this period refer to Section 6 and 7.
 

			
 
• Manage as per grade 3
 

Endocrine – Hypo and hyperthyroidism	Grade 1 (Asymptomatic)	
 
• No action
 
	
 
• Intervention not indicated
 

	Grade 2 Hyperthyroidism and Grade 2- 4 Hypothyroidism	
 
• Report overdose and liver toxicity ECIs - see Section 6 and 7.
 
• Monitor thyroid function until returned to baseline.
 
• Consider consultation with endocrinologist.
 
• Pembrolizumab can continue while on this treatment.
 
	
 
• Thyroid hormone and/or steroid replacement therapy.
 
• Hyper – non-selective beta blockers for initial therapy
 
• Hypo – thyroid hormone replacement therapy as per standard of care.
 

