Type 1 Diabetes Mellitus and ≥ grade 3 hyperglycaemia	Type 1 Diabetes Mellitus and ≥ grade 3 hyperglycaemia	
 
Report overdose and liver toxicity ECIs if appropriate see Section 6 and 7
 
Hold pembrolizumab if new onset of diabetes or grade 3-4 hyperglycaemia with evidence of beta cell failure.
 
Consultation with endocrinologist
 
Consider islet cell antibodies and antibodies to GAD, IA-2 ZnT8 and insulin.
 
	
 
Insulin replacement therapy is recommended for Type 1 diabetes mellitus and for Grade 3-4 hyperglycaemia associated with metabolic acidosis or ketonuria.
 
Evaluate patients with serum glucose and a metabolic panel, urine ketones, glycosylated haemoglobin, and C-peptide.
 

Haematologic	Grade 1 (Asymptomatic)	
 
No action
 
	
 
Intervention not indicated
 

	Grade 2	
 
Report overdose and liver toxicity ECIs within 24 hours
 
Withhold pembrolizumab, may restart if Grade 1 or resolved within 12 weeks
 
Consider Haematology consultation
 
	
 
Prednisone 1-2mg/kg daily
 
Permanently discontinue pembrolizumab if dose cannot be reduced to prednisone 10mg or less or equivalent per day within 12 weeks.
 

	Grade 3	
 
Report overdose and liver toxicity ECIs within 24 hours
 
Withhold pembrolizumab, may restart if Grade 1 or resolved within 12 weeks
 
Recommend Haematology consultation
 
	
 
IV methylprednisolone 125mg or Prednisone 1-2mg/kg p.o. (or equivalent) as appropriate.
 
Permanently discontinue pembrolizumab if corticosteroid dose cannot be reduced to prednisone 10mg or less or equivalent per day within 12 weeks.
 

	Grade 4	
 
• Report overdose and liver toxicity ECIs within 24 hours
 
• Discontinue pembrolizumab
 
• Recommend Haematology consultation
 
	
 
• IV methylprednisolone 125mg or Prednisone 1-2mg/kg p.o. (or equivalent) as appropriate.
 

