Hepatic – Drug induced Liver Injury (DILI).  Please refer to Section 6 and 7 for definitions of (DILI)	Grade 1 (Asymptomatic)	
 
• No action
 
	
 
• Intervention not indicated
 

	Grade 2	
 
• Report overdose and liver toxicity ECIs within 24 hours
 
• Withhold Pembrolizumab if AST or ALT >3.0 to 5.0 X ULN and/or total bilirubin is >1.5 to 3.0 X ULN
 
• Monitoring Liver function until values return to baseline
 
	
 
• 0.5-1mg/kg/day methylprednisolone 125mg or oral equivalent.
 
• LFT grade 1 or less initiate steroid taper for no less than 4 weeks. Consider prophylactic antibiotics and resume pembrolizumab.
 
• Permanently discontinue pembrolizumab if dose cannot be reduced to prednisone 10mg or less or equivalent per day within 12 weeks.
 
• Permanently discontinue pembrolizumab for patients with liver mets who begin treatment with grade 2 elevation of AST or ALT and AST or ALT increase ≥50% relative to baseline and lasts ≥ 1 week.
 

	Grade 3	
 
• Report overdose and liver toxicity ECIs within 24 hours
 
• Discontinue pembrolizumab if AST or ALT > 5.0 X ULN and/or total bilirubin is >3.0 X ULN
 
• Consider consultation and biopsy to establish aetiology
 
	
 
• High dose IV glucocorticosteroids for 24-48hours.
 
• Symptoms grade 1 or less initiate steroid taper for no less than 4 weeks 
 
◦ prednisone 1 to 2 mg/kg/day or dexamethasone 4mg every 4 hours.
 
 
 
• If serum transaminase levels do not decrease or symptoms worsen please refer to Section 6 and 7.
 
• Permanently discontinue pembrolizumab if dose cannot be reduced to prednisone 10mg or less or equivalent per day within 12 weeks.
 

	Grade 4	
 
• Report overdose and liver toxicity ECIs within 24 hours
 
• Discontinue pembrolizumab
 
	
 
• Manage as per grade 3
 

Neurologic	Grade 1 (Asymptomatic)	
 
• No action
 
	
 
• Intervention not indicated
 

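### The Appendix 5 steroid line for grade 2 liver injury gives a weight-based dose and a fixed 125 mg with no stated relation; section 6.5 supports only the weight-based dose

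*Combined protocol and SAP*

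**What the plan says.** The grade 2 row of the hepatic block in Appendix 5 (section 11.5) gives the steroid treatment as "0.5-1mg/kg/day methylprednisolone 125mg or oral equivalent". The only connecting word introduces the oral equivalent; none stands between the weight-based range and the fixed amount.

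Section 6.5, under immune-mediated hepatitis, gives an "initial dose of 0.5 – 1.0 mg/kg/day for grade 2 events, and 1 – 2 mg/kg/day for grade 3 or greater events", in prednisone or equivalent and followed by a taper. It contains no fixed dose. The grade 3 row of the same hepatic block calls for "High dose IV glucocorticosteroids for 24-48hours".

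Elsewhere methylprednisolone 125 mg appears in these places:
- Appendix 5, pneumonitis grades 3 and 4: "methylprednisolone 125mg IV". Table 11 in section 6.6 gives the same dose for the same grades.
- Appendix 5, colitis: "methylprednisolone 125mg IV followed by prednisone 1 to 2 mg/kg/day or dexamethasone 4mg every 4 hours". The row label is lost in the extracted text, but the row comes after the grade 2 text and the next row refers back to grade 3.
- Appendix 5, haematologic grades 3 and 4: "IV methylprednisolone 125mg or Prednisone 1-2mg/kg p.o. (or equivalent) as appropriate".

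**The concern.** One line gives two amounts of one drug and leaves the reader to decide how they fit together. For most body weights they cannot both be the daily dose.

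This is working text. Table 12 classes hepatitis and transaminase rises of grade 2 or above as events of clinical interest, and section 6.5 sends their management to Appendix 5 and a separate guidance document. Read literally, the line permits a grade 2 liver dose above the one section 6.5 sets. The same row also stops pembrolizumab for good if the steroid cannot be brought down to 10 mg of prednisone within 12 weeks, so the starting dose beside that rule ought to be clear.

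**Working it through.** **Inputs.** From the Appendix 5 line: 0.5 to 1 mg/kg/day, and 125 mg. From section 6.5: 0.5 to 1.0 mg/kg/day at grade 2, and 1 to 2 mg/kg/day at grade 3 or greater. The documents give no body weights, so 50, 70 and 90 kg are assumed. The plan has no figure of its own to reproduce.

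**Step 1. When do the two figures agree?** Weight = fixed dose ÷ dose per kg.
- Upper end of the range: 125 ÷ 1.0 = 125 kg.
- Lower end: 125 ÷ 0.5 = 250 kg.

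So 125 mg lies inside the range only between 125 and 250 kg. Both figures in the line are attached to methylprednisolone, so this step needs no conversion between drugs.

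**Step 2. What is 125 mg per kg?**

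| Assumed weight | 0.5 to 1 mg/kg | 125 mg ÷ weight |
|---|---|---|
| 50 kg | 25 to 50 mg | 2.50 mg/kg |
| 70 kg | 35 to 70 mg | 1.79 mg/kg |
| 90 kg | 45 to 90 mg | 1.39 mg/kg |

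At 70 kg, 125 mg is 125 − 70 = 55 mg to 125 − 35 = 90 mg more than the weight-based dose on any day it is given.

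**Step 3. Compare with section 6.5's hepatitis doses.** Mg for mg, 125 mg falls inside the grade 3 range of 1 to 2 mg/kg between 125 ÷ 2 = 62.5 kg and 125 ÷ 1 = 125 kg, and exceeds it below 62.5 kg. A grade 2 line can therefore be read as giving the grade 3 dose or more.

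This step does depend on conversion, because section 6.5 counts in prednisone and the Appendix 5 line names methylprednisolone. For 125 mg to stay within 1 mg/kg of prednisone, 1 mg of methylprednisolone would have to count as no more than 50 ÷ 125 = 0.40, 70 ÷ 125 = 0.56 or 90 ÷ 125 = 0.72 mg of prednisone at the three weights. The documents give no conversion factor.

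**Step 4. Which figure is out of place?** The weight-based half of the line has the same numbers as section 6.5; the 125 mg half has no counterpart there. All other uses of 125 mg are in severe-event rows. In the hepatic block, high-dose intravenous steroid is first named at grade 3. The colitis and haematologic rows that pair 125 mg with a weight-based dose also say whether one follows the other or replaces it. The hepatic grade 2 row does not.

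**The case against.** **The 125 mg may have been intended.** A linking word could have been dropped, since the colitis and haematologic rows show how such a line would read with one. Section 6.2.9.2 and section 6.5 both point to a guidance document on events of clinical interest that is not in the file and could settle the question. This stands in part. The documents show that the line is ambiguous; they make a stray figure the likelier explanation but do not prove it. A cap, loading dose or vial strength is stated nowhere, and if one was meant the line still needs words added.

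**A higher grade 2 dose is not foreign to this protocol.** For nephritis, section 6.5 says "Administer corticosteroids for grade 2 or greater events (initial dose of 1 – 2 mg/kg/day prednisone or equivalent", and 1 to 2 mg/kg/day also applies at grade 2 to pneumonitis, haematologic events and, in section 6.5 and Appendix 5, colitis. Section 6.4.1.1, by contrast, suggests 0.5 mg/kg/day for grade 2 enterocolitis. This stands, and it limits the point to a mismatch with the protocol's own hepatitis dose.

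**There is oversight.** Section 6.5 asks that immune-related events of grade 2 or higher be taken up at once with the Chief Investigator or a delegate. It is worded as advice rather than as a requirement, but it lowers the chance that the line is followed without question. It does not make the line coherent.

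**Stronger readings.** A reader might infer that 125 mg is to be given every day until taper, and multiply the excess over a week. Nothing in the documents supports a repeated 125 mg dose; where they give a sequence, it is the opening intravenous treatment. A reader might also see a matching fault in the thyroid row of Appendix 5, which mentions steroid replacement although section 6.5 treats hypothyroidism without corticosteroids. That row is shared with hyperthyroidism, and its own hypothyroid entry names thyroid hormone only, so no conflict is shown.

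**Conclusion.** The point holds as a minor dosing ambiguity. The two amounts in the line cannot both be the daily methylprednisolone dose for anyone under 125 kg. At assumed weights of 50 to 90 kg, 125 mg is about 1.4 to 2.5 times the line's stated maximum per kg. Confidence is high that the line is unclear as printed, and lower, though still favourable, that 125 mg is the figure to remove.

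The body weights are assumptions, and the comparison with section 6.5 takes methylprednisolone and prednisone mg for mg. The documents give no rate of grade 2 liver events, so no number of affected patients can be stated, and harm to patients should not be inferred. DLTs are defined by the grade and relatedness of the toxicity, not by the steroid dose used to treat it, so no DLT rule changes; nor does the sample size or any analysis.

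**What to change.** Check the line against the guidance document on events of clinical interest. Unless that document shows that the fixed dose was intended, delete the 125 mg and put the line in section 6.5's unit: *0.5-1 mg/kg/day prednisone or equivalent (oral or IV methylprednisolone)*. Removing the figure alone would leave methylprednisolone as the unit, which has not been shown to equal section 6.5's prednisone dose.

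If the guidance document does support 125 mg, state in the row whether it is a first dose, an alternative or a cap, and bring section 6.5 into line.

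The cost is one edited line in Appendix 5, carried in the next amendment, plus a sentence in section 6.5 in the second case. No procedures, visits or patients are added.

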## 11.6 Appendix 6 - Response Evaluation Criteria in Solid Tumours (RECIST) 1.1

### Criteria for Evaluating Response in Solid Tumours

RECIST version 1.1\* will be used in this study for assessment of tumour response.

\* As published: Eisenhauer et al. New response evaluation criteria in solid tumours: Revised RECIST guideline (version 1.1). Eur J Cancer 2009;45(2):228. (71)

The following paragraphs are a quick reference and the complete criteria are included in the published RECIST document also available at <http://www.eortc.be/RECIST>.

### Disease Parameters

**Measurable disease.** Measurable lesions are defined as those that can be accurately measured in at least one dimension (longest diameter to be recorded) as  $\geq 20$  mm by chest x-ray or as  $\geq 10$  mm with CT scan, MRI, or calipers by clinical exam. All tumour measurements must be recorded in millimeters (or decimal fractions of centimeters).

**Malignant lymph nodes.** To be considered pathologically enlarged and measurable, a lymph node must be  $\geq 15$  mm in short axis when assessed by CT scan (CT scan slice thickness recommended to be no greater than 5 mm). At baseline and in follow-up, only the short axis will be measured and followed.

**Non-measurable disease.** All other lesions (or sites of disease), including small lesions (longest diameter  $<10$  mm or pathological lymph nodes with  $\geq 10$  to  $<15$  mm short axis), are considered non-measurable disease. Bone lesions, leptomeningeal disease, ascites, pleural/pericardial effusions, lymphangitis cutis/pulmonitis, inflammatory breast disease, and abdominal masses (not followed by CT or MRI), are considered as non-measurable. ‘Cystic lesions’ thought to represent cystic metastases can be considered as measurable lesions, if they meet the definition of measurability described above. However, if non-cystic lesions are present in the same patient, these are preferred for selection as target lesions.

**Target lesions.** All measurable lesions up to a maximum of 2 lesions per organ and 5 lesions in total, representative of all involved organs, should be identified as target lesions and recorded and measured at baseline. Target lesions should be selected on the basis of their size (lesions with the longest diameter), be representative of all involved organs, but in addition should be those that lend themselves to reproducible repeated measurements. It may be the case that, on occasion, the largest lesion does not lend itself to reproducible measurement in which circumstance the next largest lesion which can be measured reproducibly should be selected. A sum of the diameters (longest for non-nodal lesions, short axis for nodal lesions) for all target lesions will be calculated and reported as the baseline sum diameters. If lymph nodes are to be included in the sum, then only the short axis is added into the sum. The baseline sum diameters

will be used as reference to further characterize any objective tumor regression in the measurable dimension of the disease.

Non-target lesions. All other lesions (or sites of disease) including any measurable lesions over and above the 5 target lesions should be identified as non-target lesions and should also be recorded at baseline. Measurements of these lesions are not required, but the presence, absence, or in rare cases unequivocal progression of each should be noted throughout follow-up.

## **Methods for Evaluation of Measurable Disease**

All measurements should be taken and recorded in metric notation using a ruler or calipers. All baseline evaluations should be performed as closely as possible to the beginning of treatment and never more than 4 weeks before the beginning of the treatment.

The same method of assessment and the same technique should be used to characterise each identified and reported lesion at baseline and during follow-up. Imaging-based evaluation is preferred to evaluation by clinical examination unless the lesion(s) being followed cannot be imaged but are assessable by clinical exam.

Clinical: Clinical lesions will only be considered measurable when they are superficial (*e.g.*, skin nodules and palpable lymph nodes) and  $\geq 10$  mm diameter as assessed using calipers (*e.g.*, skin nodules). In the case of skin lesions, documentation by color photography, including a ruler to estimate the size of the lesion, is recommended.

Chest x-ray: Lesions on chest x-ray are acceptable as measurable lesions when they are clearly defined and surrounded by aerated lung. However, CT is preferable.

Conventional CT and MRI: This guideline has defined measurability of lesions on CT scan based on the assumption that CT slice thickness is 5 mm or less. If CT scans have slice thickness greater than 5 mm, the minimum size for a measurable lesion should be twice the slice thickness. MRI is also acceptable in certain situations (*e.g.* for body scans). Use of MRI remains a complex issue. MRI has excellent contrast, spatial, and temporal resolution; however, there are many image acquisition variables involved in MRI, which greatly impact image quality, lesion conspicuity, and measurement. Furthermore, the availability of MRI is variable globally. As with CT, if an MRI is performed, the technical specifications of the scanning sequences used should be optimized for the evaluation of the type and site of disease. Furthermore, as with CT, the modality used at follow-up should be the same as was used at baseline and the lesions should be measured/assessed on the same pulse sequence. It is beyond the scope of the RECIST guidelines to

prescribe specific MRI pulse sequence parameters for all scanners, body parts, and diseases. Ideally, the same type of scanner should be used and the image acquisition protocol should be followed as closely as possible to prior scans. Body scans should be performed with breath-hold scanning techniques, if possible.

**PET-CT:** At present, the low dose or attenuation correction CT portion of a combined PET-CT is not always of optimal diagnostic CT quality for use with RECIST measurements. However, if the site can document that the CT performed as part of a PET-CT is of identical diagnostic quality to a diagnostic CT (with IV and oral contrast), then the CT portion of the PET-CT can be used for RECIST measurements and can be used interchangeably with conventional CT in accurately measuring cancer lesions over time. Note, however, that the PET portion of the CT introduces additional data which may bias an investigator if it is not routinely or serially performed.

**Ultrasound:** Ultrasound is not useful in assessment of lesion size and should not be used as a method of measurement. Ultrasound examinations cannot be reproduced in their entirety for independent review at a later date and, because they are operator dependent, it cannot be guaranteed that the same technique and measurements will be taken from one assessment to the next. If new lesions are identified by ultrasound in the course of the study, confirmation by CT or MRI is advised. If there is concern about radiation exposure at CT, MRI may be used instead of CT in selected instances.

**Endoscopy: Laparoscopy** The utilization of these techniques for objective tumor evaluation is not advised. However, such techniques may be useful to confirm complete pathological response when biopsies are obtained or to determine relapse in trials where recurrence following complete response (CR) or surgical resection is an endpoint.

**Tumor markers:** Tumor markers alone cannot be used to assess response. If markers are initially above the upper normal limit, they must normalize for a patient to be considered in complete clinical response. Specific guidelines for both CA-125 response (in recurrent ovarian cancer) and PSA response (in recurrent prostate cancer) have been published [JNCI 96:487-488, 2004; J Clin Oncol 17, 3461-3467, 1999; J Clin Oncol 26:1148-1159, 2008]. In addition, the Gynecologic Cancer Intergroup has developed CA-125 progression criteria which are to be integrated with objective tumor assessment for use in first-line trials in ovarian cancer [JNCI 92:1534-1535, 2000].

**Cytology, Histology:** These techniques can be used to differentiate between partial responses (PR) and complete responses (CR) in rare cases (e.g., residual lesions in tumour types, such as germ cell tumors, where known residual benign tumors can remain).

The cytological confirmation of the neoplastic origin of any effusion that appears or worsens during treatment when the measurable tumour has met criteria for response or stable disease is mandatory to

differentiate between response or stable disease (an effusion may be a side effect of the treatment) and progressive disease.

**FDG-PET:** While FDG-PET response assessments need additional study, it is sometimes reasonable to incorporate the use of FDG-PET scanning to complement CT scanning in assessment of progression (particularly possible 'new' disease). New lesions on the basis of FDG-PET imaging can be identified according to the following algorithm:

- a. Negative FDG-PET at baseline, with a positive FDG-PET at follow-up is a sign of PD based on a new lesion.
- b. No FDG-PET at baseline and a positive FDG-PET at follow-up: If the positive FDG-PET at follow-up corresponds to a new site of disease confirmed by CT, this is PD. If the positive FDG-PET at follow-up is not confirmed as a new site of disease on CT, additional follow-up CT scans are needed to determine if there is truly progression occurring at that site (if so, the date of PD will be the date of the initial abnormal FDG-PET scan). If the positive FDG-PET at follow-up corresponds to a pre-existing site of disease on CT that is not progressing on the basis of the anatomic images, this is not PD.
- c. FDG-PET may be used to upgrade a response to a CR in a manner similar to a biopsy in cases where a residual radiographic abnormality is thought to represent fibrosis or scarring. The use of FDG-PET in this circumstance should be prospectively described in the protocol and supported by disease-specific medical literature for the indication. However, it must be acknowledged that both approaches may lead to false positive CR due to limitations of FDG-PET and biopsy resolution/sensitivity.

Note: A 'positive' FDG-PET scan lesion means one which is FDG avid with an uptake greater than twice that of the surrounding tissue on the attenuation corrected image.

